5. GENERAL METHODOLOGY AND CONVENTIONS

5.1. Hypotheses and Decision Rules

5.1.1. Hypotheses and Sample Size

The primary objective of this study is to evaluate the treatment effect with inotuzumab ozogamicin, by demonstrating a greater CR/CRI rate than that observed with historical control. The statistical hypotheses for the primary endpoint CR/CRI per investigator's assessment are the same as those used in global pivotal Phase 3 Study B1931022, where based on review of the literature published historical data, the expected CR/CRI rate with historical control in the combined first and second salvage setting was approximately 37%. The observed results in the control arm in Study B1931022 didn't exceed 37% either. The study will test the null hypothesis H_0 : CR/CRI rate per investigator's assessment $\leq 37\%$ vs the alternative hypothesis H_a : CR/CRI rate $> 37\%$.

A single-stage design will be used to test the null hypothesis (H_0) with 1-sided 0.025 significance level. A sample size of 44 patients is planned to provide at least 90% power to reject the null hypothesis (H_0 : CR/CRI rate $\leq 37\%$) when the true CR/CRI rate $\geq 61\%$ under the 1-sided significance level 0.025, based on single binomial proportion test under normal approximation with empirical estimate for variance.

A sufficient number of participants will be screened to ensure 44 participants enrolled and received at least one dose of inotuzumab ozogamicin.

5.1.2. Decision Rules

Assuming exactly 44 participants as planned in [Section 5.1.1](#) are enrolled and take at least one dose of treatment, the null hypothesis will be rejected and it will be concluded that the study has demonstrated that the true CR/CRI rate exceeds 37% if 23 or more responders are observed. However, at the time of the analysis, the testing will depend on the actual number of participants enrolled.

5.2. General Methods

Except the hypothesis testing for CR/CRI, all analyses will be descriptive.

5.2.1. Data Handling after the Cutoff Date

Data after the cutoff date may not undergo the cleaning process and will not be displayed in any listings or used for summary statistics, statistical analyses or imputations.

5.2.2. Pooling of Data Across Centers

In order to provide overall estimates of treatment effects, data will be pooled across centers. A variable for 'center' will not be included in statistical models or for subgroup analyses since it is anticipated that there will be a high number of participating centers with a small number of participants randomized/treated at each center.

5.2.3. Definition of Study Day

The study day for assessments occurring on or after the first dose of study treatment (eg, adverse event onset, tumor measurement) will be calculated as:

$$\text{Study day} = \text{Date of the assessment/event} - \text{start date of inotuzumab ozogamicin} + 1.$$

The study day for assessments occurring prior to the first dose of study treatment (eg, baseline characteristics, medical history) will be negative and calculated as:

$$\text{Study day} = \text{Date of the assessment/event} - \text{start date of inotuzumab ozogamicin}.$$

The study day will be displayed in all relevant data listings.

5.2.4. Definition of Cycle and Cycle Day

Cycle start and end dates are derived per participant and not per study treatment.

Study drug inotuzumab ozogamicin is administered once every week for 3 weeks (on Days 1, 8, and 15) for each cycle. Except for Cycle 1 where a 7-day treatment free interval is optional, all other cycles have such an interval following the 3 treatment administrations and hence the nominal cycle length is 21-28 days for cycle 1 and 28 days for other cycles. A participant can only go through 6 cycles at most.

- For Cycle X, the actual cycle start date for each participant is:
 - The earliest start date of dosing in the Cycle X day 1 visit CRF exposure page, if the participant received study treatment on that visit (ie, any study drug with dose>0 at that visit).
 - The first day of assessments in the Cycle X day 1 visit, if the participant did not receive study treatment on that visit (ie, all study drugs had dose=0 at that visit). Use start date in the exposure page if available; if start date is not available then use date of collection of vital signs on Cycle X day 1 visit.
- For all but the last cycle,
 - Actual cycle stop date is calculated as the start date of the next cycle minus one day.
 - Actual cycle duration is calculated from Day 1 of a cycle to the day prior to Day 1 of the next cycle, as follows:

$$\text{Actual Cycle Duration (weeks)} = (\text{cycle stop date} - \text{cycle start date} + 1) / 7.$$

- For the last cycle, actual cycle duration is the planned cycle duration and actual cycle stop date is calculated as min(actual cycle start date + 28 – 1 day, new anti-cancer therapy date-1, death).

The cycle day will be calculated as:

Cycle day = Date of the assessment/event – cycle start date + 1.

5.2.5. Definition of Start of New Anti-cancer Therapy

Start date of new anti-cancer therapy is used to determine the end of the on-treatment period (see [Section 3.5](#)).

The start date of new anti-cancer therapy is the earliest date after first dose of inotuzumab ozogamicin amongst the following:

- Start date recorded in the ‘Follow-up Cancer Therapy’ eCRF pages.
- Start date of radiation therapy recorded in ‘Follow-up Radiation Therapy’ eCRF pages.
- Start date of surgery recorded in ‘Follow-up cancer surgery’ eCRF pages.

When start date of anti-cancer therapy is missing or partially missing, the imputation rules described in [Section 5.3.3.4](#) should be applied

Start date of new induction therapy is used for censoring in efficacy analyses, and it is defined as

- Start date of “INDUCTION” subcategory recorded in the ‘Follow-up Cancer Therapy’ eCRF pages.

5.2.6. Date of Last Contact

The date of last contact will be derived for participants not known to have died at the data cutoff date using the latest complete date (ie, imputed dates will not be used in the derivation) among the following:

- All assessment dates (eg, blood draws (laboratory, Pharmacokinetics (PK)), vital signs, physical exam, performance status, ECG, tumor assessments);
- Start and stop dates of concomitant therapies including non-drug treatments or procedures;
- Start and end dates of anti-cancer therapies administered after study treatment discontinuation including systemic therapy, radiation, and surgeries;
- AE start and end dates;

- Last date of contact collected on the ‘Survival Follow-up’ CRF (do not use date of survival follow-up assessment unless status is ‘SUBJECT REMAINS IN FOLLOW-UP ’);
- Study treatment start and end dates;
- Date of discontinuation on disposition CRF pages (do not use if reason for discontinuation is lost to follow-up or death).

Only dates associated with actual examinations of the participant will be used in the derivation. Dates associated with a technical operation unrelated to participant status such as the date a blood sample was processed or dates data were entered into the CRF will not be used. Assessment dates after the data cutoff date will not be applied to derive the last contact date.

5.2.7. ALL Disease Assessment Date

The date of ALL disease assessment at each nominal timepoint as provided by the investigator on the ALL response assement CRF will be utilized for the respective analyses.

5.2.8. Adequate Baseline ALL Disease Assessment

Subject had an adequate baseline tumor assessment if the subject had the following two procedures at screening: bone marrow biopsy or aspirate with blasts $\geq 5\%$; hematology test with presence of peripheral blast cells (% or absolute).

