#### Type of Participant and Disease Characteristics:

2. Relapsed or refractory CD22-positive ALL ( $\geq 5\%$  marrow blasts, assessed by morphology) due to receive either salvage 1 or salvage 2 therapy and for which treatment with inotuzumab ozogamicin offers a reasonable treatment option.
3. Ph+ ALL patients must have failed treatment with at least 1 tyrosine kinase inhibitor and standard multi-agent induction chemotherapy.
4. Patients in Salvage 1 with late relapse should be deemed poor candidates for reinduction with initial therapy.
5. Patients with lymphoblastic lymphoma and bone marrow involvement  $\geq 5\%$  lymphoblasts by morphologic assessment.
6. ECOG performance status 0-2.
7. Adequate liver function, including total serum bilirubin  $\leq 1.5 \times$  ULN unless the patient has documented Gilbert syndrome, and aspartate and alanine aminotransferase (AST and ALT)  $\leq 2.5 \times$  ULN. If organ function abnormalities are considered due to tumor, total serum bilirubin must be  $\leq 2 \times$  ULN and AST/ALT  $\leq 2.5 \times$  ULN.
8. Serum creatinine  $\leq 1.5 \times$  upper limit of normal (ULN) or any serum creatinine level associated with a measured or calculated creatinine clearance of  $\geq 40$  mL/min.
9. Male and female patients of childbearing potential and at risk for pregnancy must agree to use a highly effective method of contraception throughout the study and for a minimum of 8 months (females) and 5 months (males) after the last dose of assigned treatment. A patient is of childbearing potential if, in the opinion of the Investigator,

he/she is biologically capable of having children and is sexually active. Female subjects of nonchildbearing potential must meet at least 1 of the following criteria:

- a. Achieved postmenopausal status, defined as follows: cessation of regular menses for at least 12 consecutive months with no alternative pathological or physiological cause; and have a serum follicle stimulating hormone (FSH) level confirming the postmenopausal state;
- b. Have undergone a documented hysterectomy and/or bilateral oophorectomy;
- c. Have medically confirmed ovarian failure.

All other female subjects (including female subjects with tubal ligations) are considered to be of childbearing potential.

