**Prior/Concomitant Therapy:**

17. Prior chemotherapy within 2 weeks before enrollment with the following exceptions:
  - a. To reduce the circulating lymphoblast count or palliation: steroids, hydroxyurea or vincristine;
  - b. For ALL maintenance: mercaptopurine, methotrexate, vincristine, thioguanine, and/or tyrosine kinase inhibitors.

18. Patients must have recovered from acute non hematologic toxicity (to  $\leq$ Grade 1) of all previous therapy prior to enrollment.
19. Prior monoclonal antibodies within 6 weeks of enrollment, with the exception of rituximab which must be discontinued at least 2 weeks prior to Cycle 1 Day 1.
20. Prior allogeneic hematopoietic stem cell transplant (HSCT) or other anti-CD22 immunotherapy  $\leq$ 4 months before enrollment. Patients must have completed immunosuppression therapy for treatment of graft versus host disease (GvHD) prior to enrollment. At enrollment, patients must not have  $\geq$ Grade 2 acute GvHD, or extensive chronic GvHD.
21. Administration of live vaccine  $\leq$ 6 weeks before enrollment.

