**Diagnostic Assessments:**

23. Peripheral absolute lymphoblast count  $\geq$ 10,000 / $\mu$ L (treatment with hydroxyurea and/or steroids/vincristine is permitted within 2 weeks of Cycle 1 Day 1 to reduce the white blood cell [WBC] count).
24. Known systemic vasculitides (eg, Wegener's granulomatosis, polyarteritis nodosa, systemic lupus erythematosus), primary or secondary immunodeficiency (such as human immunodeficiency virus [HIV] infection or severe inflammatory disease).
25. Current or chronic hepatitis B or C infection as evidenced by hepatitis B surface antigen and anti-hepatitis C antibody positivity, respectively, or known seropositivity for HIV. HIV testing may need to be performed in accordance with local regulations or local practice.
26. QTcF  $>$ 470 msec (based on the average of 3 consecutive electrocardiograms [ECGs]).

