### 8.2. Efficacy Assessments

Assessment of response and progression status will be evaluated according to a modified Cheson Criteria described in [Section 10.7 Appendix 7](#). Disease assessments are determined using information from bone marrow evaluations, laboratory assessments (eg, hematology), clinical and radiological information (eg, extramedullary disease). No bone marrow aspirate is necessary if non-response or progressive disease can be diagnosed from peripheral blood evaluation or radiological/clinical assessment. Patients with extramedullary disease prior to first dose will have radiographic assessment (computed tomography [CT] or magnetic resonance imaging [MRI]) to confirm a CR or CRI using the same method of assessment, unless contraindicated. CT scan with contrast is the preferred method of assessment.

Bone marrow aspirates (or biopsies if clinically indicated) and disease assessments (See [Section 10.7, Appendix 7](#)) will be performed at screening, at day 16-28 of cycles 1, 2 or until CR/CRI and MRD negativity are achieved. Then after every 1, 2 cycles as clinically indicated, and at end-of-treatment (EOT) visit (unless previously done within 28 days).

Bone marrow aspirates will be analyzed at the study site. A bone marrow (BM) biopsy will be done in patients achieving CRi by the investigator's assessment to evaluate cellularity.

Complete blood count (CBC) with differential and platelets, bone marrow aspirate, bone marrow biopsy as clinically indicated, plus re-evaluation of pre-existing or suspected extramedullary disease as clinically indicated should be completed at the time of each disease assessment. If a CNS disease assessment was indicated during screening, reassessments will be done as clinically indicated. ([Table 1](#)).

At any time point, an additional aspirate or biopsy may be required if the original aspirate is inadequate for disease assessment.

- For patients requiring baseline cytoreduction or palliation (eg, hydroxyurea, steroids and/or vincristine), a post-cytoreduction BM assessment is not required prior to enrollment.
- If a patient receives a more aggressive chemotherapy regimen (ie, another salvage attempt), the patient must repeat the entire screening process and must meet all eligibility criteria prior to enrollment.
- G-CSF should be discontinued at least 72 hours prior to every bone marrow assessment.

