	
analyzed. And the MRD-negativity will be defined as malignant B lymphocytes occurring at a frequency of <math><10^4</math>.
 

• The number and percentage of patients with MRD negativity in patients achieving CR/CRI will be summarized descriptively with corresponding two-sided 95% CI. This analysis is based on responders in the As-Treated population.

 
PFS
 

• PFS will be defined as the time from date of first dose to the date of disease progression (ie, objective progression, relapse from CR/CRI), or death due to any cause, whichever occurs first.

• Using the Kaplan-Meier method, plot the estimation of the survival function and estimate its associated statistics on PFS (including the median PFS with two-sided 95% CI, the PFS rates at clinical meaningful timepoints with two-sided 95% CI) for all participants received at least one dose of investigational product without regard to discontinuation from treatment. This analysis is based on As Treated population. Patients without a PFS event at time of analysis will be censored at the date of last valid disease assessment. Patients with documentation of a PFS event after an unacceptably long interval (>28 weeks if there was post-baseline disease assessment, or >12 weeks if there was no post-baseline assessment) since the previous disease assessment will be censored at the date of the previous assessment (date of first dose if no postbaseline assessment). The CI for the median PFS will be calculated according to Brookmeyer and Crowley method, and the CIs for the survival function estimates at the timepoints will be derived using the log(-log) method

• A sensitivity analysis of PFS will be based on defining PFS as the time from date of first dose to the date of disease progression (ie, objective progression, relapse from CR/CRI, treatment discontinuation due to global deterioration of health status), death due to any cause, or starting new induction therapy/post-therapy HSCT without achieving CR/CRI, whichever occurs first (including post-study treatment follow-up disease assessments).

 
OS
 

• OS will be defined as the time from first dose to death due to any cause.

• Using the Kaplan-Meier method, plot the estimation of the survival function and estimate its associated statistics on OS

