6.2.2. Progression-Free Survival

6.2.2.1. Main Analysis

Progression-Free Survival (PFS) is defined as the time from date of first dose to the date of the first documentation of disease progression (ie, objective progression, relapse from CR/CRi) as assessed by the investigator, or death due to any cause, whichever occurs first.

Estimand strategy: Hypothetical strategy. The analysis will consider intercurrent events of start of subsequent new induction therapy and an extended gap in tumor assessment prior to an assessment of disease progression or death.

Analysis set: Safety analysis set.

Intercurrent events and missing data: Partial dates will be imputed as described in [Section 5.3](#). No other imputations for missing data will be performed. PFS data will be censored as follows:

- For participants who start a new induction therapy (as defined in [Section 5.2.5](#)) prior to an event, censoring will be at the last adequate tumor assessment prior to the start of new induction therapy. Note: if date of progression occurs on the same date as the start of new induction therapy, the progression will be counted as an event.
- For participants who do not have an adequate baseline tumor assessment or any post-baseline tumor assessments, censoring will occur on the date of first dose unless death occurred on or before 12 weeks after first dose in which case the death will be considered an event.
- For participants having adequate baseline tumor assessment and without defined PFS events, censoring will occur on the date of last valid disease assessment (date of first dose if no post-baseline assessment).
- For participants with defined PFS events occurring after an unacceptable long interval (>28 weeks if there was post-baseline disease assessment, or >12 weeks if there was no post-baseline assessment) since the previous disease assessment, censoring will occur at the date of the previous assessment (or date of first dose if there is no post-baseline assessment).

Analysis methodology: The Kaplan-Meier method will be used to plot the estimated survival function and estimate its associated statistics on PFS (including the median PFS with two-sided 95% CI, the PFS rates at clinical meaningful timepoints with two-sided 95% CI) for safety analysis set without regard to discontinuation from treatment.

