6.2.3. Duration of Remission

Duration of remission (DoR) is defined as the time from date of first response in responders (CR/CRI) to the date of disease progression (ie, objective progression, relapse from CR/CRI), death due to any cause, whichever occurs first (including post-study treatment follow-up).

The censoring rules for DoR are as described for PFS in Section 6.2.2.1, but the censoring occurs on the date of first dose for PFS analysis will occur on the date of first remission of responders for DOR analysis.

The Kaplan-Meier method will be used to plot the estimated survival function and estimate its associated statistics on DoR (including the median DoR with two-sided 95% CI) for responders to investigational product without regard to discontinuation from treatment.

This analysis is based on responders in the safety analysis set.

The CI for the median DoR will be calculated according to Brookmeyer and Crowley method.

Duration of Complete Remission (DoCR) and Duration of Complete Remission with Incomplete Hematologic Response (DoCRI) will also be analyzed separately in the safety analysis set following the same methods described above. DoCR is defined as the time from the date of CR in participants who achieved a CR to the date of disease progression (ie, objective progression, relapse from CR/CRI) as assessed by the investigator, or death due to any cause, whichever occurs first. DoCRI is defined as the time from the date when a CRI is first achieved to the date of disease progression (ie, objective progression, relapse from CR/CRI) as assessed by the investigator, or death due to any cause, whichever occurs first. The censorship of DoCR and DoCRI follows the same as DoR.

Note that DoCRI is the same as DoR for CRI participants.

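### SAP 5.2.8, applied as worded, makes the baseline of an eligible patient without circulating blasts inadequate, which would drop observed PFS and DoR events; separately, protocol and SAP differ on whether an inadequate baseline is primary non-response

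*SAP*

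**What the plan says.** **Definition.** SAP 5.2.8 requires two screening procedures for an adequate baseline: a marrow biopsy or aspirate with at least 5% blasts, and a "hematology test with presence of peripheral blast cells (% or absolute"). It is the only definition in the two documents. The protocol uses the idea in 9.3 (per-protocol population) and 9.4.1 but does not define it.

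**Consequence in the SAP.** Section 6.2.2.1 states: "For participants who do not have an adequate baseline tumor assessment or any post-baseline tumor assessments, censoring will occur on the date of first dose". A death within 12 weeks of first dose is the exception and counts as an event. Table 2 puts an inadequate baseline first among seven censoring reasons, and the PFS sensitivity analysis in 6.2.2.2 keeps the rule. Section 6.2.3 carries the PFS rules over to DoR: "the censoring occurs on the date of first dose for PFS analysis will occur on the date of first remission of responders for DOR analysis".

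**Protocol on PFS.** Section 9.4.1 has no inadequate-baseline rule for PFS or DoR. For PFS it says: "Patients without a PFS event at time of analysis will be censored at the date of last valid disease assessment".

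**Eligibility.** Inclusion criterion 2 asks for at least 5% "marrow blasts, assessed by morphology) due to receive either salvage 1 or salvage 2 therapy". Exclusion criterion 23, "Peripheral absolute lymphoblast count", sets only an upper limit (10,000/µL). Exclusion criterion 17 exempts certain drugs from the chemotherapy washout: "To reduce the circulating lymphoblast count or palliation: steroids, hydroxyurea or vincristine". Protocol 8.2 adds that for patients so treated "a post-cytoreduction BM assessment is not required prior to enrollment".

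**Primary endpoint.** Protocol 9.4.1 counts four groups as non-responders: death before the first post-baseline assessment, an inadequate baseline, new anti-cancer therapy before that assessment, and no post-baseline assessment at all. SAP 6.1.1.1 gives the same list without the inadequate baseline. The SAP's summary of changes (Table 1) does not mention the omission.

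**The concern.** The blood element of SAP 5.2.8 can be read in two ways: blasts must be found in the blood, or a blast result must be recorded. The first follows the wording, and the parallel marrow element is itself a result threshold. On that reading a patient can meet every entry criterion, have a qualifying marrow and a complete blood count, and still fail the definition because the blood is free of blasts. The protocol even permits drugs before enrolment that lower the circulating count.

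That patient's progression, relapse or death after 12 weeks would then not enter the PFS analysis, although it was observed. The remission would contribute zero follow-up to DoR. The loss is uneven in PFS: among flagged patients early deaths stay as events, while everyone else leaves the risk set at time zero. The PFS sensitivity analysis would not reveal this, because it uses the same rule.

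The difference between the two non-responder lists is a separate matter and exists on either reading. It concerns the only endpoint that is tested.

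**Working it through.** **1. The plan's own figures.** With null rate 0.37, alternative 0.61, one-sided alpha 0.025 and 90% power, the Wald formula gives n = (1.960 + 1.282)² × 0.61 × 0.39 / 0.24² = 43.4, so 44. The Wald z is 1.72 at 22/44 and 2.03 at 23/44, so 23 is the critical count. The exact probability of at least 23 responders at a true 61% is 0.909. The plan reproduces.

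**2. PFS if blasts must be found.** From the documents: N = 44; data cutoff at least 9 months after the last first dose (SAP 2); follow-up to 2 years; the 12-week death exception (84 days = 2.76 months). Assumed, because the documents do not give them: blast-free share f of 10% to 40%, independent of outcome; exponential PFS with median 5 months; 30% of PFS events are deaths; censoring uniform on 9 to 24 months.

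- Hazard λ = ln 2 / 5 = 0.1386 per month.
- Probability of an observed event, unflagged patient: 1 − (e^(−9λ) − e^(−24λ)) / (15λ) = 0.879.
- Probability of a retained event, flagged patient (death within 12 weeks): 0.3 × (1 − e^(−2.76λ)) = 0.095.
- Expected events: 44 × [(1 − f) × 0.879 + f × 0.095].
- Approximate widening of standard errors: √(38.7 / expected events).
- Large-sample Kaplan-Meier median: up to 12 weeks the hazard is λ[(1 − f) + 0.3f]e^(−λt) / [(1 − f)e^(−λt) + 0.3f(e^(−λt) − e^(−2.76λ))]; after that it is λ.

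| Blast-free share | Expected PFS events | SE ratio | Median (months) |
|---|---|---|---|
| 0% | 38.7 | 1.00 | 5.00 |
| 10% | 35.2 | 1.05 | 4.92 |
| 20% | 31.8 | 1.10 | 4.83 |
| 30% | 28.3 | 1.17 | 4.71 |
| 40% | 24.9 | 1.25 | 4.56 |

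Over assumed medians of 4 to 7 months and death shares of 20% to 50%, the median falls by 0.05 to 0.13 month at a 10% share and by 0.29 to 0.77 month at 40%. In simulation at N = 44 with nobody flagged, 95% of estimated medians lie between 3.2 and 7.4 months, so the shift is small by comparison. The cost is mainly lost events.

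**3. DoR if blasts must be found.** Protocol Table 4 gives 73.2% CR/CRi and a median DoR of 5.3 months for all randomized patients on inotuzumab ozogamicin in study B1931022. Responders contributing follow-up: 44 × 0.732 × (1 − f) = 32.2 at f = 0, and 29.0 down to 19.3 at 10% to 40%. With exponential durations and censoring uniform on 8 to 23 months (assumed), expected events fall from 27.3 to between 24.5 and 16.4. The early-death exception is ignored here.

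**4. If a recorded value is enough.** A screening count of zero blasts qualifies, no such patient is censored at time zero, and every effect in steps 2 and 3 is nil.

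**5. The list difference.** Under the SAP list as written, the chance of 23 or more responders at a true 61% stays at 0.909. If k treated patients truly lack an adequate baseline and are counted as failures, it becomes P(Bin(44 − k, 0.61) ≥ 23): 0.878, 0.838 and 0.790 for k = 1, 2 and 3. At a true 73.2% it stays at or above 0.994.

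**The case against.** The best reply is that SAP 5.2.8 means a recorded result. It speaks of procedures, and a choice between percentage and absolute value describes how a number is reported. Protocol Table 10 includes a blast count in the hematology panel, and its footnote 1 uses the same choice as a recording rule. The 5% marrow threshold mirrors an entry criterion, while no entry criterion asks for circulating blasts. This reading is as plausible as the other, and it stands. It does not remove the point, because no text decides between the two and the programmer must choose.

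It is also fair that the size rests on assumptions, that SAP 5.2 makes everything except the CR/CRi test descriptive, and that both documents let the SAP modify the protocol. The absence of a baseline censoring rule in the protocol's PFS and DoR text is therefore context, not a conflict. On the list difference, marrow and blood remission are judged on post-baseline values, so leaving the item out is defensible; only major changes to the primary analysis call for an amendment, and nothing shows that this one is major. What remains is an unexplained mismatch.

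A reader might go further and infer that primary power collapses. Applying the protocol's list together with the requirement that blasts be found would give a counted rate of 0.61 × 0.9 = 0.549 at a 10% blast-free share, and a probability of 0.693 of reaching 23. The documents do not support this as a description of the plan: the SAP's primary analysis does not use an inadequate baseline at all. The figure shows only why the definition should be settled before the lists are aligned.

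**Conclusion.** The point holds as a minor one, in two parts. First, the wording of SAP 5.2.8 is open. Applied as written, it would discard observed PFS and DoR events from eligible patients: about 9% to 36% of expected PFS events (3.5 to 13.8 of 38.7) at an assumed blast-free share of 10% to 40%. Early deaths remain as events in PFS, so not every such patient is censored at time zero. The median moves little against its sampling spread. If a recorded value is meant, the effect is zero. It would be too strong to say that the SAP does exclude these patients; the text allows that reading but does not force it.

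Second, protocol 9.4.1 and SAP 6.1.1.1 disagree on whether an inadequate baseline is primary non-response. That holds on either reading. A treated patient who truly lacks a baseline assessment should be rare, and the SAP list as written leaves primary power as planned.

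The sizes rest on the assumed share, its independence of outcome, exponential times and the assumed split of PFS events; the textual findings do not.

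**What to change.** Before database lock, in this order:

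(a) In SAP 5.2.8, reword the blood element to *hematology test with a peripheral blast result (% or absolute) reported, zero allowed*. This costs one phrase and no new data. If that was the intention already, nothing else changes.

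(b) Once (a) is in place, add *inadequate baseline assessment* to the non-responder list in SAP 6.1.1.1 so that it matches protocol 9.4.1, and record the change in the SAP's summary of changes. The protocol already contains the item, so no amendment is needed. The downside is a slightly stricter primary count if a treated patient truly lacks an adequate baseline: with one such patient, the chance of 23 or more responders at a true 61% is 0.878 instead of 0.909.
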